4.0 ELIGIBILITY CRITERIA

4.1 Inclusion Criteria:

1. Histologically confirmed prostate adenocarcinoma with metastasis either starting or recently started on LHRH analogue therapy. [Late induction permitted within 3 months of starting LHRH analogue therapy or antiandrogen] All patients who have not initiated hormone therapy (Early induction patients) must have elevated PSA ≥ 4 ng/ml within 28 days prior to registration. For late induction registrations, PSA must be ≥ 4 ng/ml prior to start of androgen deprivation therapy; either antiandrogen or LHRH analogue or GNRH antagonist .If patients are on antiandrogen, this will need to be discontinued for at least 7 days prior to registration.
2. Patients with a history of prior neoadjuvant or adjuvant hormone therapy are eligible provided they have received twenty four or less months of hormone treatment (single or combination treatment, excluding orchiectomy). Neoadjuvant/adjuvant hormone therapy must have been discontinued at least 6 months prior to registration. This is intended to exclude patients who might have been rendered indirectly androgen insensitive.
3. There must be no plans to receive concomitant chemotherapy, biological response modifiers, radiation therapy or hormonal therapy. Concomitant radiation therapy is allowed for the palliation of severe pain/neuropathic compression.
4. Prior or concomitant use of megestrol acetate for the treatment of hot flashes is allowed.
5. Patients must have a performance status of 0 - 2 by Zubrod Criteria.
6. Patients must have recovered from any major infections and/or surgical procedures and, in the opinion of the investigator, not have significant active medical illness precluding protocol treatment or survival.
7. No prior malignancy is allowed except for adequately treated basal cell (or squamous cell) skin cancer, superficial or in situ cancer of the bladder. For an invasive cancer the patients should be disease free for at least 3 years prior to enrollment on study.
8. For all patients a bone scan must be performed within 60 days prior to registration for tumor assessment. CT scans (abdomen and pelvis) and chest x-ray are optional, but must be repeated if used for disease assessment. For late induction registrations, tumor assessment imaging showing metastatic disease must be available prior to start of androgen deprivation therapy.
9. Age 18 or older and willing and able to provide informed consent.

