Karmanos Cancer Institute. Training and support will be provided for all staff entering data. Data entry must occur within 2 weeks of visits along with submission of applicable source documentation. The only concomitant medication data to be submitted is administration of bisphosphonate or denosumab.

5.2 Stratification and randomization procedures:

The registering data manager will first stratify the patient by race (AA or other) and cancer related bone pain at diagnosis of metastatic disease (present or absent) into one of 4 strata. Even if pain is well controlled/resolved at present the patient will be considered positive for bone pain. The patient will then be randomized to Arm A or Arm B using the stratum-appropriate randomization list prepared in advance by the study statistician [name]. Arms A and B are defined in the Study Schema (on page 5) and in Section 5.3 below. Each of the 4 randomization sequences will use random permuted blocks of varying sizes. The treatment arm randomization and enrollment confirmation will be communicated to site staff in writing within 24-48 hours from receipt of all eligibility source documents. Study treatment should start within 7 days of registration.

5.3 Study design and plan:

Overall Study Design and Plan

This study is a multicenter Phase II, randomized, screening study of oral MDV3100 (160 mg/day) in patients with metastatic hormone sensitive prostate cancer. Patients must not have received prior cytotoxic chemotherapy for metastatic disease. Radiation therapy, and initiation of

bisphosphonates or other approved bone targeting agents, and standard of care steroid and pain management are allowed and should not result in discontinuation of study drug therapy.

For patients eligible for late induction registration the treatment start date will be the date of initiation of GNRH analogue or antagonist, with or without antiandrogen. Late induction patient visits will be adjusted based on the length of their prior hormone therapy. Study drug therapy should be continued as long as the patient is tolerating the study drug and continues androgen deprivation therapy or until confirmed radiographic disease progression or a skeletal related event AND one of the two following events: 1) initiation of another agent for treatment of prostate cancer. Or 2) Intolerance to therapy.

Patients will be randomized to receive either:

ARM A

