| creat | X | X | | | X | | | X | | X | |
| PT/INR ² | X | X | X | X | X | X | X | X | X | X | |
| PSA | X | X | X | X | X | X | X | X | X | X | |
| Testosterone | X | | | | X | | | X | | X | |
| CXR/CT ³ | X | | | | | | | X | | | |
| Bone ³ scan | X | | | | | | | X | | | |
| OS | | | | | | | | | | | X |
| Progression | | X | X | X | X | X | X | X | X | | X |
| Tumor biopsy ⁵ | X ⁵ | | X ⁵ | | | | | | | | |
| CTC ⁵ | | X ⁵ | X ⁵ | | | | | | | | |

1. Pre-study H & P, labs, EKG may be done within 28 days of registration. If Labs, and H and P are done within 72 hours prior to registration=they do not have to be repeated on day 1 of therapy unless clinically indicated.
2. PT, INR to be done only if patient on therapeutic Coumadin and then will need to be repeated at least once every month.
3. Tumor assessment scans must be within 60 days prior to registration for all patients. Bone scans are required for pretreatment and subsequent tumor assessments. CT/MRI of abdomen and pelvis should be done if necessary for tumor assessment. Radiologic assessment with bone scans should be done at 6 and

12 months on study (+/- 1 month) and then annually (+/- 1 month) as long as patient continues on study treatment. For late induction registrations, tumor assessment imaging showing metastatic disease must be available prior to start of androgen deprivation therapy.

4. After completion of therapy patients will be followed every 3 months for disease status and survival.
5. Fresh tissue should be collected pre-therapy. Archival tissue should be submitted within 28 days of registration. Post treatment tumor biopsy (optional) and CTC can be conducted within 28-42 days after registration even for late induction patients. Late induction patients will get CTC at time of study entry and then 28-42 days later.
6. Disease progression is defined as evidence of radiographic progression, a skeletal-related event, or clinical progression. Progression of measurable disease is defined by RECIST 1.1 criteria, or progression of bone metastases or occurrence of new skeletal related event or by PSA per PCWG 2 criteria [Appendix B].

8.0 CRITERIA FOR EVALUATION AND ENDPOINT DEFINITION:

The RECIST 1.1 criteria with unidimensional measurement are to be used for measurable disease response evaluation [14].

Baseline Disease Assessment

Measurable lesions must be accurately measured in at least one dimension

(longest diameter in the plane of measurement is to be recorded) with a minimum size of:

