8.4 Duration of stable disease

Stable disease is measured from the start of the treatment until the criteria for progression are met, taking as reference the smallest measurements recorded since the treatment started. Tumor evaluations are recommended every three cycles while on protocol therapy and then as clinically required by the treating physician.

8.5 Time to Treatment Failure:

From date of registration to date of progressive disease, or date patient is taken off study for any reason. All patients, regardless of the number of completed cycles of therapy, will be included for toxicity evaluation. All subjective toxicities encountered during the study will be evaluated according to the NCI toxicity criteria. Objective toxicities will be based upon the greatest severity that occurred at any time during a treatment cycle and not on the severity noted at the beginning of the next cycle.

8.6 Time to Progression:

From date of registration to date of progressive disease, defined as either progression of measurable disease by RECIST 1.1 criteria, or progression of bone metastases or occurrence of new skeletal related event or by PSA per PCWG 2 criteria [Appendix B].

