8.12 Skeletal-related event

Defined as occurrence of new pathologic bone fractures (vertebral or nonvertebral), spinal cord compression, requirement of surgery or radiation therapy to bone metastases (including the use of radioisotopes), or a requirement to change antineoplastic therapy to treat bone pain or other related symptoms.

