8.13 Circulating Tumor Cells Response

The outcome measures associated with this definition are the following:

Measurements of CTC counts pre-therapy, post-therapy and the change between time points. To assess the pre-therapy circulating tumor cell (CTC) counts and the changes in CTC after 1 month of therapy, and to associate them with the primary endpoint. CTC counts will be measured at baseline (day 1), and month 1 (days 28-42) of therapy. The pre and post-therapy CTC counts ; $<5/7.5$ ml which is considered favorable, vs $>5/7.5$ ml which is considered unfavorable, have been shown to be prognostic in metastatic CRPC patients treated with cytotoxic chemotherapy.

8.14 Correlative tests:

Androgen metabolism enzymes: ERG, CXCR4, Androgen biosynthetic enzymes: Testing will be conducted on paraffin embedded fixed tissue. Analysis will be performed by Immunohistochemistry. Scoring will be between 0 to 3 and will be done by 2 independent experienced investigators.

Androgen biosynthetic enzymes: ERG, CXCR4 testing is conducted on RNA from frozen tumor tissue biopsies. RNA message measurement by qualitative and quantitative RT- PCR (real time PCR). Qualitative Scoring for RT-PCR is the presence or absence of band (+/-) when an amplified PCR mixture is run on gel. Quantitative PCR is the level of expression of the test gene will be expressed in in terms of folds.

Genomic testing:

AR splice variants: Starting material is frozen tissue. Analysis is RNA message quantitation by RT-PCR and QPCR, which is similar to androgen biosynthesis analysis: Qualitative (+/-) and quantitative results (copy number) will be obtained.

9.0 CRITERIA FOR REMOVAL FROM STUDY:

- 9.1 Intercurrent illness which would, in the judgment of the investigator, a) affect assessments of clinical status to a significant degree, b) require discontinuation of drug, or c) both a and b.
- 9.2 Receiving any other treatment, investigational agent or alternative therapy directed at prostate cancer.
- 9.3 Unacceptable toxicity
- 9.4 Disease progression
- 9.5 Delay in treatment of \geq 2 months
- 9.6 The patient may withdraw from the study at any time for any reason.
- 9.7 In the judgment of the investigator, further treatment would not be in the best interest of the patient.

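### Bone radiation keeps a patient on drug under 5.3 but removes him under 9.4; separately, no month 6 or 7 PSA is scheduled after early removal and 11.6.1 does not say how he is scored

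*Combined protocol and SAP*

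**What the plan says.** **Radiation and stopping study drug.** The 5.3 sentence that ends "standard of care steroid and pain management are allowed and should not result in discontinuation of study drug therapy" has radiation therapy as its first item. Inclusion criterion 3 agrees: "Concomitant radiation therapy is allowed for the palliation of severe pain/neuropathic compression". The stopping rule in 5.3 continues drug "until confirmed radiographic disease progression or a skeletal related event AND one of the two following events", the two being a new prostate cancer agent or intolerance.

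**Radiation as progression.** Section 8.12 includes in its definition of a skeletal-related event (SRE) the "requirement of surgery or radiation therapy to bone metastases". Time to progression in 8.6 counts the "occurrence of new skeletal related event or by PSA per PCWG 2 criteria". Footnote 6 of the Section 7.0 calendar says: "Disease progression is defined as evidence of radiographic progression, a skeletal-related event, or clinical progression". The removal list in Section 9.0 has the entry "9.4 Disease progression" with no exception. The schema and 5.3 both say that therapy continues past month 7 unless a Section 9.0 criterion is met.

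**PSA after removal.** The calendar marks PSA at pre-study, day 1, each of months 1 to 7, and every 3 months after that. The PSA cell in the off-study column is blank. Footnote 4 and 8.9 provide follow-up every 3 months for disease status or progression and for survival.

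**Endpoint and analysis sets.** Section 8.1 sets the endpoint at month 7 of protocol therapy. Section 8.10 calls a patient evaluable after seven months of androgen deprivation with month 6 and month 7 PSA values. Section 11.6.1 analyses all randomized patients and, separately, the evaluable ones. It gives no rule for a missing month-7 PSA.

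**The concern.** There are two separate problems.

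First, one event, palliative radiation to a bone metastasis, carries two instructions. A site following 5.3 keeps the patient on study drug and on monthly PSA. A site following 9.4 removes him. Six institutions are expected to enrol and may differ. Bone pain is a stratification factor, so the situation is foreseeable.

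Second, removal before month 7 for any Section 9.0 reason, including "9.3 Unacceptable toxicity", takes the patient off the schedule that supplies the primary endpoint. The loss is avoidable. Section 8.10 counts months of androgen deprivation, not of study drug, so a man who stops enzalutamide or bicalutamide but stays on LHRH therapy could be evaluable if his PSA were drawn. Without it he leaves the evaluable set on which N is based, and his place in the all-randomized analysis rests on an inference. Sites know the assigned arm, so the rule should be fixed before data are seen. Removal can also differ by arm: Section 6.0 requires permanent discontinuation for any reported seizure activity in enzalutamide patients.

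**Working it through.** **1. The radiation conflict (no arithmetic).**

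| Step | Source | Result for bone radiation alone |
|---|---|---|
| Radiation is allowed and should not stop drug | 5.3; inclusion 3 | Continue |
| An SRE without a second event | 5.3 stopping rule | Continue |
| Radiation to bone metastases is an SRE | 8.12 (also 8.7) | SRE |
| A new SRE is progression | 8.6; calendar footnote 6 | Progression |
| Progression is a removal criterion | 9.4 | Remove |

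The or/AND in the 5.3 rule can be grouped two ways: (progression or SRE) AND a second event, or progression or (SRE AND a second event). Under either, an SRE alone does not stop drug, so the conflict does not depend on the grouping. Radiation to a site other than a bone metastasis is not an SRE and raises no conflict.

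**2. The plan's sample size.** Inputs from 11.5: 50% v 75%, one-sided alpha 0.10, power 0.80, 1:1. The two-proportion formula with continuity correction gives 41 per arm, as stated (33 without the correction). Then 41/0.90 = 45.6, rounded up to 46 per arm, also as stated.

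**3. Power formula for the scenarios.** With n_A, p_A and n_B, p_B the size and rate in each arm, and p the pooled rate:

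power = Φ{[p_A − p_B − ½(1/n_A + 1/n_B) − 1.2816·SE0] / SE1}

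SE0 = √[p(1−p)(1/n_A + 1/n_B)]; SE1 = √[p_A(1−p_A)/n_A + p_B(1−p_B)/n_B]

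At 50% v 75% this gives 0.845 at 46 per arm, 0.804 at 41, 0.786 at 39 and 0.755 at 36. Losing numbers alone costs little.

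**4. Evaluable set, selective loss.** The removal rates q_A and q_B are assumptions. Suppose every removed patient is a true non-remitter without a PSA. The evaluable rates become 0.75/(1−q_A) and 0.50/(1−q_B), on 46(1−q) patients per arm.

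| q_A / q_B | Arm A | Arm B | Difference (points) | Power |
|---|---|---|---|---|
| 0 / 0 | 75.0% | 50.0% | 25.0 | 0.845 |
| 5% / 5% | 78.9% | 52.6% | 26.3 | 0.871 |
| 2% / 10% | 76.5% | 55.6% | 21.0 | 0.714 |
| 10% / 2% | 83.3% | 51.0% | 32.3 | 0.964 |

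For the third row: n_A = 45.08, n_B = 41.4, difference 0.2098, correction 0.0232, SE0 = 0.1016, SE1 = 0.0997. So (0.2098 − 0.0232 − 1.2816 × 0.1016)/0.0997 = 0.565, and Φ(0.565) = 0.714.

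**5. All-randomized set.** If removed non-remitters are scored as no remission, the rates stay at 75% and 50% in every row above, with power 0.845. The remaining risk is a remitter scored as a failure because no PSA was drawn. Two such patients in Arm A only (75% − 2/46 = 70.7%) lower power to 0.706; two in each arm lower it only to 0.834.

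**The case against.** **Section 5.3 already settles the radiation question.** It is the specific rule, it names radiation, and a site could reasonably give it precedence. That is a fair reading, but no text states the precedence, and 5.3 itself sends the reader to Section 9.0 for withdrawal. The point stands for bone metastases only. A reader might infer that any palliative radiation triggers removal; the SRE definition does not support that.

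**The endpoint already covers removed patients.** Section 8.1 refers to month 7 of protocol therapy, and a man off protocol therapy has no such month, so he is naturally a non-remitter among all randomized. This has force. A reader might infer that the all-randomized rate is open by as much as 5/46 = 10.9 points per arm, using the plan's own allowance for non-evaluable patients. Section 8.1 makes that too strong. What remains is that 11.6.1 does not state the rule, and that 8.10 points the other way by counting androgen deprivation rather than study drug.

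**Some PSAs will be drawn anyway.** Section 6.0 asks for monthly PSA over the first 8 visits without tying it to study drug, and off-study progression checks may include PSA. Neither gives an off-study patient a draw timed to months 6 and 7. A patient removed between the two visits lacks only the second.

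**Collecting PSA off drug could credit an arm with the effect of a later therapy.** This is correct, and the scoring rule has to deal with it.

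**The power figures are chosen scenarios.** Also correct. They run in both directions, and the plan claims only 0.80 at 41 per arm, not 0.845.

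**Conclusion.** Both parts hold in a limited form. The conflict between 5.3 and 9.4 is in the current text, applies to radiation to bone metastases, and decides whether such a patient stays on study drug. The PSA gap applies to anyone removed before month 7, whatever the reason. The likely scoring of such a patient can be inferred from 8.1 but is not written into the analysis.

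The size of the effect is unknown, because the documents give no early-removal rate and no frequency of bone radiation. A reader might infer that the primary comparison is biased in a known direction or that the trial is underpowered. The documents support neither. Under the assumed removal rates, and with all removals being non-remitters, the evaluable-set difference falls to 21.0 points or rises to 32.3 depending on which arm loses more. Balanced loss changes little, and the all-randomized analysis is unaffected if those patients are scored as no remission. The exposure is to uneven loss, and to remitters scored as failures for want of a blood draw. The stated sample size is correct for its assumptions.

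**What to change.** 1. In 9.4, state that palliative radiation to bone metastases does not by itself remove a patient or stop study drug. It still counts as an SRE, and as a progression event for the time-to-event endpoints defined to include it.
2. In the Section 7.0 calendar, schedule month 6 and month 7 PSA for every randomized patient who agrees, whether or not study drug has stopped.
3. In 8.1 and 11.6.1, state that in the all-randomized analysis a patient is scored as no remission if he starts another prostate cancer therapy before month 7, or if his month-7 PSA is still missing. The first clause prevents credit for a later therapy; the second fixes the rule in advance. Item 2 keeps the number scored this way small.

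The cost is wording in four places and at most two PSA draws per patient removed before month 7. With 92 patients and assumed removal of 2%, 5% or 10%, 2 × 92 × q gives at most about 4, 9 or 18 draws in the whole trial. N does not change.

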The major toxic effect of bicalutamide is moderate diarrhea which is very rarely severe (exclusion of other causes of diarrhea should be considered in severe cases).

The dose modifications for this will be as follows, if diarrhea is attributed to protocol therapy.

1. Grade 2 diarrhea, treat symptomatically with anti-diarrhea drugs.
2. Grade 2 diarrhea unresponsive to symptomatic treatment or Grade 3/4 diarrhea - discontinue bicalutamide/enzalutamide until complete recovery.

ABNORMAL LIVER FUNCTION TESTS (AST, ALT, BILIRUBIN)

Grade 2 or greater toxicity - Stop bicalutamide/enzalutamide; wait until liver function tests (LFTs) including AST/ALT and bilirubin are normal (Grade 1 or less).

Restart treatment when AST/ALT and bilirubin return to normal/baseline. If toxicity (Grade 2 or worse) occurs again, discontinue protocol treatment.

Patients requiring treatment delay greater than 2 months for any reason should be removed from protocol treatment.

Patients may complain of flatulence, bloating and mild "gas pains" which should not result in changes in treatment. Symptomatic treatment should be employed with antacids, simethicone, etc. Unexpected or fatal toxicities (including suspected reactions) assessed by the investigator to be related to study therapy/ies must be reported per serious adverse event reporting guidelines as mentioned.

7.0 STUDY CALENDAR: Visit dates and scans can be within +/- 7 days of planned dates.

Study treatment must start within 7 days of registration. For patients eligible for late induction registration the treatment start date will be the date of initiation of GNRH analogue or antagonist, with or without antiandrogen.

| Test | Pre study ¹ | Day 1 | Mth 1 | Mth 2 | Mth 3 | Mth 4 | Mth 5 | Mth 6 | Mth 7 | Post Mth 7 | F/U ⁴ |
|---------------------------|------------------------|----------------|----------------|-------|-------|-------|-------|-------|-------|--------------|------------------------|
| | | | | | | | | | | Every 3 mths | Every 3 mths off study |
| Hand P | X | X | X | X | x | | | X | X | X | |
| PS | X | X | X | X | X | | | X | X | X | |
| Tox | | | X | X | X | | | X | X | X | |
| VS | X | X | X | X | X | | | X | X | X | |
| EKG | X | | | | | | | | | | |
| CBC | X | X | | | X | | | X | | X | |
| AST | X | X | | | X | | | X | | X | |
| ALT | X | X | | | X | | | X | | X | |
| Alk phos | X | X | | | X | | | X | | X | |
| BUN | X | X | | | X | | | X | | X | |
| lytes | X | X | | | X | | | X | | X | |

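### The calendar leaves out three of the eight toxicity evaluations that Section 6.0 requires; on the ADT clock, the latest late-induction entrants may also go 12-13 weeks without scheduled vital signs

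*Combined protocol and SAP*

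**What the plan says.** **Toxicity, all patients.** Section 6.0 requires monthly toxicity evaluation across the first eight visits, counting Day 1 as the first, and every three months after that until progression. The Tox row in Section 7.0 has marks at months 1, 2, 3, 6 and 7 and in the three-monthly column. Day 1, month 4 and month 5 are empty. The PSA row, by contrast, is filled at every visit from pre-study onward: "PSA | X | X | X | X | X | X | X | X | X | X".

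**Physical checks.** The H&P row reads "Hand P | X | X | X | X | x | | | X | X | X", that is, pre-study, Day 1, months 1, 2, 3, 6, 7 and three-monthly, with months 4 and 5 empty. The performance-status and vital-sign rows follow the same pattern.

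**Late induction.** Section 4.1 (item 1) admits patients up to 3 months after starting an LHRH analogue or antiandrogen. For them, Sections 5.3 and 7.0 say that "the treatment start date will be the date of initiation of GNRH analogue or antagonist, with or without antiandrogen". Section 5.3 adds: "Late induction patient visits will be adjusted based on the length of their prior hormone therapy". Section 7.0 also says "Study treatment must start within 7 days of registration" and "Visit dates and scans can be within +/- 7 days of planned dates". Footnote 5 makes an exception for two items: the optional biopsy and "CTC can be conducted within 28-42 days after registration even for late induction patients". It then says "Late induction patients will get CTC at time of study entry and then 28-42 days later".

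**The concern.** The first problem is a direct conflict between text and table. Site staff usually work from the table. A site that does so would skip evaluations that the text requires, and those evaluations feed secondary objective 4, the comparison of toxicity rates by arm.

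The second arises when a calendar that thins out after month 3 is shifted by the length of prior ADT. A patient who receives his first randomised dose at ADT month 3 joins the calendar just as the monthly physical checks stop. Blood pressure is a named enzalutamide risk: Section 2.0 reports hypertension or raised pressure in 6.6% against 3.3% on placebo. Section 4.2 (item 7) excludes patients only above 170 systolic or 105 diastolic. Section 3.1 puts steady state at Day 28 with about 8.3-fold accumulation. For this patient the one scheduled reading before month 6 is at Day 1, before the drug has accumulated.

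**Working it through.** **1. Toxicity row against Section 6.0.** The first eight visits are Day 1 and months 1 to 7, so 1 + 7 = 8. The Tox row marks months 1, 2, 3, 6 and 7, which is 5 of 8. Three are missing: Day 1 as baseline, and months 4 and 5 on treatment. This does not depend on the clock, because months 4 and 5 follow study entry even for a month-3 entrant. As an upper bound, if all 92 planned patients (Section 11.5.1) reached month 5 and every site followed the table, 2 × 92 = 184 on-treatment evaluations would be omitted.

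**2. Which clock applies to late induction.** For the ADT clock: the start-date rule appears in both Section 5.3 and Section 7.0; visits are shifted for prior therapy; footnote 5 needs an explicit exception to run CTC and biopsy from registration; and Section 8.10 defines evaluability by seven months of androgen deprivation. Against it: *adjusted* is not defined; Section 8.1 places the endpoint at the seventh month of protocol therapy; footnote 3 times bone scans by months on study; and several Section 4.2 items equate Day 1 with enrolment. The balance favours the ADT clock. Steps 3 and 4 are conditional on it.

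**3. Scheduled vital-sign and H&P checks after Day 1.** Months on drug = calendar month − ADT months at first dose, using calendar months 1, 2, 3, 6 and 7, with one month = 30.44 days.

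| Prior ADT at first dose (months) | Checks, in months on drug | Checks in first 84 days on drug |
|---|---|---|
| 0 | 1, 2, 3, 6, 7 | 2 |
| 1 | 1, 2, 5, 6 | 2 |
| 2 | 1, 4, 5 | 1 |
| 2.5 | 0.5, 3.5, 4.5 | 1 |
| 2.75 | 0.25, 3.25, 4.25 | 1 |
| 3 | 3, 4 | 0 |

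**4. Length of the full gap.** The 3-month limit is ADT day 3 × 30.44 = 91.3. Dosing may follow registration by up to 7 days, so first dose can fall as late as day 98.3. Month 6 is day 182.6.

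- First dose on day 91.3: 182.6 − 91.3 = 91.3 days, 13.0 weeks.
- First dose on day 98.3: 182.6 − 98.3 = 84.3 days, 12.0 weeks.
- With ±7 days on the month-6 visit: 77.3 to 98.3 days, about 11 to 14 weeks.

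Dosing at or after the month-3 visit needs registration on about ADT day 84-91, the last week of the limit. If the visit window lets the month-3 visit and Day 1 be taken together a week early (day 84.3), the affected period widens to about two weeks. The nominal gap is then 182.6 − 84.3 = 98.3 days, 14.0 weeks, and would reach 15.0 only if month 6 were also a week late.

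**The case against.** The strongest reply has four parts.

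- *The interval is not unusual here.* Every patient goes without vital signs from month 3 to month 6, and checks are three-monthly after month 7. The documents do not say when blood-pressure rises occur. This stands as far as it goes: early clustering cannot be claimed. But other patients have at least one on-drug check before that interval begins, and early-induction patients have three. The month-3 entrant has none.
- *Section 6.0 already covers months 4 and 5.* It does require toxicity to be evaluated then. PSA and progression are also marked monthly, CTC is drawn 28-42 days after entry, and SAEs are reported from registration. This stands as partial cover. None of these schedules a blood-pressure reading, and the Tox cells at those two visits are among the blanks.
- *The clock is uncertain.* If visits are counted from first dose, the vital-sign gap disappears. This stands, and is why the point is conditional. The Tox conflict is unaffected.
- *Few patients, perhaps none.* This also stands. Only those in Arm A would carry the enzalutamide risk.

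A reader might infer that late-induction patients in general have no safety follow-up for three months. The documents do not support that. Patients with 2 months or less of prior ADT are still checked by about 1 month on drug, and the contacts listed above continue for everyone.

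**Conclusion.** The text-table conflict on toxicity evaluation is certain and applies to all patients in both arms: the calendar shows five of eight required evaluations. How many would actually be missed depends on which source sites follow, which the documents do not say.

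The vital-sign and H&P gap of about 12-13 weeks (11-14 with visit windows) is arithmetically right under three assumptions: visits follow the ADT clock; prior therapy began with the GNRH agent, so that the 3-month limit and the clock share an origin; and registration falls in about the last one to two weeks of that limit. The documents do not state the share or timing of late-induction entry, so the number affected is unknown and may be zero.

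It would go too far to conclude that early hypertension will be missed, or that the results are biased. The documents give no timing for blood-pressure rises. The blank cells apply equally to both arms, and the monthly PSA schedule behind the primary endpoint is complete. No effect on the endpoint, power or primary comparison is claimed. This is a minor safety-monitoring improvement, worth making because it is cheap.

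**What to change.** 1. In the Section 7.0 calendar, mark Tox at months 4 and 5, and at Day 1 as a baseline, to match Section 6.0. This is three cells and adds nothing that Section 6.0 does not already require.
2. Add a calendar footnote: late-induction patients have at least vital signs and toxicity assessed at about 1 and 2 months after the first randomised dose, at the monthly PSA visits already scheduled. Keep every existing visit, including months 6 and 7.
3. In the same footnote, say what *adjusted* means in Section 5.3, so that sites apply one clock.

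For a month-3 entrant the added assessments fall at ADT months 4 and 5, so he is checked at 1, 2, 3 and 4 months on drug instead of first at 3. Added vital-sign assessments per patient are 0 with 1 month of prior ADT, 1 with 2 months, and 2 with 2.5 to 3 months. Timing is approximate for entry between whole months: at 2.5 months of prior ADT, the checks fall at 1.5 and 2.5 months on drug. The downside is therefore at most two brief assessments per such patient. The footnote does not require a full H&P, so a PSA visit need not become a longer one. If visits are in fact counted from first dose, those vital-sign checks are already scheduled and the footnote adds none. Laboratory tests, dosing and endpoint timing do not change.
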